#### - Any increase in hepatocyte ballooning score

#### 5.3.11.3 Resolution of NASH

Resolution of NASH in primary estimand is defined as meeting both criteria below.

- Lobular inflammation score  $\leq 1$
- Hepatocyte ballooning = 0

#### 5.4 Statistical models

#### 5.4.1 Logistic regression model for primary and key secondary analysis

Hierarchical testing procedure and the hypothesis tests at each step for primary and key secondary analyses are defined in Section 2.5 and Section 2.6.

For binary dependent variable and considering the link of NASH with many metabolic risk factors, a logistic regression model is used to allow more flexibility in adjusting for both categorical and continuous explanatory variables.

The efficacy of LIK066 for NASH is postulated due to its ability to improve obesity and diabetes. Frequently regarded as two manifestations of metabolic syndrome, T2DM and NAFLD commonly exist together with, for example, insulin resistance as one of the key pathological factors. The randomization of this study is stratified by patient's T2DM status at baseline. Links between obesity and histologic NASH were also well known (Lassailly et al 2015, Vilar-Gomez et al 2015).

improvement					
Study	Intervention	population	Histologic endpoint	effect	
Vilar-Gomez	Weight loss	Obese w.	Resolution of NASH	p <0.01ª	
et al 2015	by life style change	NASH	Fibrosis status	p<0.00ª	
Lassailly et al	Bariatric	Obese w.	NASH resolution	85%	
2015	surgery for	NASH	Fibrosis improvement	p<0.0001 b	
	weight loss		Ballooning	p<0.0001 b	

**Table 5-4**Association of weight loss with NASH resolution or liver fibrosisimprovement

a: p-value based on Cochran-Mantel-Haenszel  $\chi^2$  trend test between weight loss categories and the histologic endpoint stratified by age older than 55 years, sex, type 2 diabetes, BMI>=35

Lobular inflammation

p<0.0001b

b: p-value based on Wilcoxon signed rank test for paired data before and 1 year after bariatric surgery

Hence BMI and T2DM status are anticipated to be prognostic of histologic changes, with or without therapeutic intervention, and will be included in the logistic regression model as confounding factors.

Novartis	For business use only	Page 42
SAP		CLJN452D12201C

LJN452 is anticipated to improve liver fibrosis, with or without NASH resolution, based on previous studies of other FXR modulators (Neuschwander Tetri et al 2015, Younossi 2019). The baseline stage of fibrosis is a plausible prognostic factor for histologic response, especially for the fibrosis improvement itself, and included also as a factor in the logistic regression model.

#### Table 5-5 FXR modulation for NASH resolution or fibrosis improvement

			Patients with histologic improvement in NASH over control		
Study	Intervention (Target/MOA)	Population	Endpoint	Diff. over control	Statistical significance
FLINT (Neuschwander	Obeticolic acid (FXR / NAFLD)	Borderline or definite NASH	Fibrosis improvement	35% vs. 19%	p=0.004ª
et. Al. 2015)			Resolution of definite NASH	22% vs. 13%	p=0.08ª
			Hepatocellular ballooning improvement	46% vs. 31%	p=0.03 ª
			Lobular inflammation improvement	53% vs. 35%	p=0.006 ª
			Portal inflammation improvement	12% vs. 13%	p=0.90 ª
REGENERATE (Youinossi 2019)	OCA 25mg (FXR/ NASH)	NASH w stage 2/3 fibrosis	Fibrosis improvement w/o NASH worsening	21% vs. 10.6%	p=0.0002 b
			NASH resolution w/o fibrosis worsening	11.7% vs. 8.0%	p=0.1268 b

a: p-value based on Cochran-Mantel-Haenszel  $\chi^2$  trend test stratified by clinic and diabetes status

b: no details on calculation of p-value in the press release

The logistic regression model assumes patient's week 48 histological response status  $y \in (0, 1)$ ~ binomial (1,  $p_{jklm}$ ), where  $p_{jklm}$  is the probability of histologic response and related to the collection of factors/covariates *X* corresponding to patient's study treatments *j*, baseline fibrosis stage *k*, baseline T2DM status *l* and baseline BMI *m* through logit link function (Nelder and Wedderburn 1972)

For patients sampled in this study, it follows that  $\log \left(\frac{p_i}{1-p_i}\right) = \boldsymbol{\beta}^T \boldsymbol{X}_i$  for i=(1, 2, ..., n), where n is the sample size of the study and  $\boldsymbol{\beta}$  is the vector of coefficients to be estimated for the effects of independent variables.

Under the aforementioned binomial distribution, the probability function can be derived as

$$f(y_i) = p_i^{y_i} (1 - p_i)^{1 - y_i}$$

with log likelihood function

$$l = \sum_{i=1}^{n} (y_i \log(p_i) + (1 - y_i) \log(1 - p_i))$$

where  $p_i = \frac{\exp(\beta^T X_i)}{1 + \exp(\beta^T X_i)}$ 

The basic maximum likelihood estimators (MLE) $\hat{\beta} \sim N(\beta, I(\beta)^{-1})$ , where  $I(\beta)$  is the Fisher's information matrix, for such logistic regression model is known to suffer from small sample bias. Given the uncertainties on benefits of LJN452 and LIK066 over placebo effects (Table 3-1), the penalized likelihood method proposed by Firth (1993) will be adopted to reduce potential small-sample bias and to consistently produce finite MLEs in case of complete or quasicomplete separations during the calculations.

Over-dispersion associated with the estimation of variances for binomial data will be corrected using the Williams method (1982).

With randomization and blinding, the possibility of collinearity between study treatment and other independent variables can be reasonably ignored so inflation on standard errors of the coefficients for treatment effect is not expected in the analysis model despite potential collinearity among other cofactors.

# 5.4.1.1 Interactions among independent variables and subgroup analysis

It is possible that the different mechanisms of actions with LJN542 and/or LIK066 may lead to differential effects on the components of the primary endpoints, which is potentially an advantage achieved with combination therapy. If such differential effects exist, however, it may also lead to interactions between covariates and main treatment effect, which is not included in the primary analysis model.

The statistical inference of primary analysis is on the overall patient population targeted by this study, notwithstanding the possibility of such granular modulation of the treatment effect. Nevertheless, better understanding on what limits or enhances the add-on effect of the combination therapy, and for whom or under what circumstances it exists, could inform decisions on future development of the combination therapy.

Considering the sample size of the study and unknown treatment effects, adding additional interaction effect in the logistic model could increase the risk of small sample (small number of events/non-events within class) bias and failures to converge. Hence subgroup analysis as outlined in Section 2.13.1 will be performed.

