# 1.1 Study design

[figure not shown]
This is a randomized, double-blind, parallel-group, multiple-arm study to assess the efficacy, safety and tolerability of tropifexor and licogliflozin combination therapy compared to each monotherapy in patients with non-alcoholic steatohepatitis (NASH) and advanced fibrosis.

The study consists of 1) a screening period, 2) a treatment period starting from randomization on Day 1 and running to Week 48, and 3) a follow-up period of 4 weeks after the last dose of study treatment. The screening period starts from the time of the signing informed consent and continues for up to 8 weeks when all inclusion/exclusion criteria have been evaluated and all baseline assessments have been performed. The study duration from first dose of study medication is 52 weeks. The total duration of participation may be up to 60 weeks.

Approximately 210 patients with NASH and F2-F3 fibrosis will be randomized in a 1:1:1 ratio to one of the following treatments:

- Arm A: tropifexor + licogliflozin combination therapy,
- Arm B: tropifexor monotherapy,
- Arm C: licogliflozin monotherapy

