# 2.2.1 Subgroup of interest

Exploratory analysis on the primary endpoint (Section 2.13.1) will be performed on following subset of FAS.

[figure not shown]
- FAS with baseline fibrosis stage of F2
- FAS with baseline fibrosis stage of F3
- FAS with T2DM at baseline
- FAS without T2DM at baseline
- FAS asian (Based on race collected on the Demographics CRF page)
- FAS non-asian (Based on race collected on the Demographic CRF page)

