#### Table 3-1Placebo effects on histological responses

The response rates for the monotherapies are deemed less likely to exceed 30%. For the stepwise gatekeeping testing procedure adopted for primary analysis, total sample size of 210 (70:70:70) is chosen so that there is approximately 80% power for the first hypothesis test (combination vs licogliflozin) if the true add-on effect is 20% for combination therapy.

Table 3-2	Power under different assumptions of mono and combination therapy
	effect sizes

True response rate assumptions		Add-on effect size in 1 st	power of 1-sided hierarchical tests α=0.05		
Licogliflozin	Tropifexor	Combination	test	1 st test	Both tests
30%	30%	38%	8%	25%	12%
23%	23%	33%	10%	38%	22%
30%	30%	44%	14%	53%	34%
30%	30%	47%	17%	67%	52%
23%	30%	41%	18%	75%	34%
20%	20%	40%	20%	84%	75%
25%	25%	45%	20%	80%	69%
30%	30%	50%	20%	79%	67%
30%	30%	51%	21%	82%	72%
23%	30%	46%	23%	89%	60%

Power calculations were performed with simulations (n=100000) implemented in R 3.3.3, where the primary analysis in each simulated study was performed using z-tests of difference in proportions without continuity correction for simplicity.

The dropout rate of the study is anticipated to be around 10%. Because early termination and missing response data will be incorporated into the primary analysis with multiple imputations, no adjustment for early dropouts from study were implemented for the sample size calculations.

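### SAP 5.4.1.1 declines a treatment-by-subgroup term for small-sample reasons that apply at least as much to the subset analyses it relies on, and no visible text plans an estimate of the difference between subgroups

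*SAP*

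**What the plan says.** SAP Section 5.4.1.1 accepts that treatment effects may vary with covariates. It keeps the primary inference on the overall population, and says that knowing in which patients the add-on effect exists could inform later development. It then argues that "adding additional interaction effect in the logistic model could increase the risk of small sample" bias and failure to converge, and concludes: "Hence subgroup analysis as outlined in Section 2.13.1 will be performed".

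SAP Section 2.2.1 gives the subsets: "Exploratory analysis on the primary endpoint (Section 2.13.1) will be performed on following subset of FAS". They are baseline F2, baseline F3, T2DM, no T2DM, Asian and non-Asian. Section 2.13.1, which both places cite for the method, is not in the public text.

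Two other parts of the SAP bear on the stated reason. Section 5.4.1 adopts Firth's penalised likelihood to limit small-sample bias and keep estimates finite under separation. Section 2.5.2 expects no convergence problem once Firth is used.

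The SAP describes the three-arm design: "Approximately 210 patients with NASH and F2-F3 fibrosis will be randomized in a 1:1:1 ratio". The current protocol (Section 6.1.3) has 380 participants in four arms.

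**The concern.** Asking in whom the effect exists is asking about a difference between subgroups. The SAP sets aside the term that estimates this difference because the data are sparse, and instead divides the same data into smaller pieces. Refitting a logistic model in each half of a split is the same as one model in which every covariate, not only treatment, interacts with the split. That does not reduce the small-sample problem.

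If subset results are shown without an estimate of their difference, readers are left to compare intervals by eye. At these sizes that is a poor guide. What is at stake is the interpretation of an exploratory analysis that the SAP itself links to development decisions. The primary test is not affected.

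**Working it through.** **The plan's own power figure.** SAP Section 3.1 gives "approximately 80% power for the first hypothesis test (combination vs licogliflozin) if the true add-on effect is 20% for combination therapy". Table 3-2 is headed "power of 1-sided hierarchical tests α=0.05", and the simulations behind it were run "using z-tests of difference in proportions without continuity correction for simplicity". For 30% vs 50% with 70 per arm:
- pooled SE = sqrt(2 × 0.40 × 0.60 / 70) = 0.0828
- unpooled SE = sqrt((0.25 + 0.21)/70) = 0.0811
- power = Φ((0.20 − 1.645 × 0.0828)/0.0811) = Φ(0.79) = 0.784

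Simulation gives 0.789, against 79% in the table. The figure reproduces. The documents give no figure for the subgroup work.

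**Parameter count, three arms, split by fibrosis stage** (T2DM is the same). This assumes the subset analysis refits the model of SAP 2.5.2.
- Each separate fit: intercept + 2 treatment + T2DM + BMI = 5. The pair has 10.
- One interaction model: intercept + 2 treatment + fibrosis + T2DM + BMI + 2 interactions = 8.
- Asian/non-Asian (race is not in the primary model): 6 each, 12 for the pair, against 9.
- Four arms, fibrosis or T2DM: 6 each, 12 for the pair, against 10.

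**Events per parameter.** SAP Section 3.1 says "The response rates for the monotherapies are deemed less likely to exceed 30" per cent. Taking 30/30/50% with 70 per arm, events = 70 × (0.30 + 0.30 + 0.50) = 77.
- Interaction model: 77/8 = 9.6.
- Separate fit, even split: 38.5/5 = 7.7.
- Separate fit in a 20% subgroup: 15.4/5 = 3.1.
- Four arms at the protocol's Table 12-3 rates for fibrosis improvement: 140 × 0.35 + 80 × 0.30 + 80 × 0.30 + 80 × 0.20 = 113 events. This gives 113/10 = 11.3 against 56.5/6 = 9.4 at an even split.

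The documents give no subgroup shares, so all splits here are assumptions.

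**Convergence** (1,000 simulated trials, 210 patients, three arms, 15% subgroup).
- Ordinary maximum likelihood: 9.3% of separate fits failed, against 8.4% of interaction fits.
- Firth: none failed by either route.

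**Standard errors at 50% vs 30%, 70 per arm.** The log odds ratio is ln(0.5/0.5) − ln(0.3/0.7) = 0.847.
- Overall: sqrt(1/(70 × 0.25) + 1/(70 × 0.21)) = 0.354.
- Each half: 0.354 × √2 = 0.500.
- Difference between halves: 0.354 × 2 = 0.708.

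**Same true effect in both halves.**
- Chance that one half's 95% CI excludes 1: Φ(0.847/0.500 − 1.96) = Φ(−0.27) = 0.395.
- Chance that exactly one does: 2 × 0.395 × 0.605 = 0.48.
- Simulation with the Firth model (1,500 trials): 46%. In the same setting the interaction estimate had |z| > 1.96 in about 4% of trials.

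**Power of the interaction.** If it is as large as the whole effect: Φ(0.847/0.708 − 1.96) = Φ(−0.76) = 0.22, two-sided 0.05.

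**Does the route change the subgroup estimates?** Hardly. Under Firth at an even split, the mean subgroup log odds ratio was 0.873 from the joint model and 0.874 from the separate fit, with standard deviations 0.508 and 0.509. Mean standard errors were 0.517 and about 0.52.

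**The case against.** The strongest objection is that the method sits in Section 2.13.1, which is withheld. It may refit the model, give only descriptive rates, or already compare subgroups. This stands: the parameter count is conditional on a refit, and a reader may not infer that the plan lacks a heterogeneity estimate. What can be read is the decision in 5.4.1.1 and the reason given for it.

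Second, keeping interactions out of the confirmatory model is ordinary practice. That also stands, and nothing here asks for them there.

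Three stronger readings are tempting, and the documents do not support them:
- That subset analyses cannot show whether the effect differs. Two disjoint subsets give independent log odds ratios that can be subtracted. In simulation the subtracted estimate correlated 0.99 with the joint-model interaction, and the |z| > 1.96 result agreed in 99% of trials.
- That every subset fit is the larger model. One fit has 5 parameters against 8; only the pair has more.
- That development would be steered by chance about half the time. The 46% to 48% is the rate at which an informal comparison of intervals would mislead. The SAP plans no such rule, labels the work exploratory, and in Section 2.1 reports p-values only for formal tests.

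Finally, the SAP predates the current protocol and foresees amendment (Section 1.1). That affects when to make the change. The argument holds for both designs.

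**Conclusion.** The point holds in a limited form. Small-sample bias and non-convergence do not justify preferring subset analyses to a treatment-by-subgroup term. If the model is refitted, the pair of fits uses 10 parameters against 8, on fewer patients per fit, and Firth already answers the convergence worry. The visible plan states a question about differences between subgroups without a visible estimate of one. Whether Section 2.13.1 supplies it cannot be checked.

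The practical size is modest. Subgroup estimates barely move by either route, and the comparison has only about 22% power even for an interaction as large as the full effect. The benefit is that an imprecise difference would be shown as imprecise, where side-by-side intervals would disagree about half the time with no true difference. That figure rests on an assumed even split, 70 per arm and 50% vs 30%.

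**What to change.** Keep the primary model unchanged. For the exploratory subgroup work, fit the same Firth logistic model on the whole FAS with a treatment-by-subgroup term, one factor at a time, adding a race main effect for Asian/non-Asian. Report the odds ratio in each subgroup and the ratio of odds ratios with its 95% CI, labelled exploratory and without a p-value. If Section 2.13.1 already gives subset estimates, it is enough to add the ratio of odds ratios with its CI. Remove the small-sample and convergence reason from 5.4.1.1.

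The cost is a few lines of SAP text and one added term per model (two for race), which can go into the revision that the four-arm design needs anyway. Two limits should be stated beside the results. The interaction estimate is imprecise. And the imputation model in SAP 5.4.2 excludes treatment, so imputed outcomes will tend to pull the ratio of odds ratios towards 1.

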#### 5.4.2 Multiple imputation for missing primary and key secondary analysis

MI method for missing data allows the flexibility of including additional auxiliary variables in the imputer model and accounts for the uncertainty on real value with multiple inputted values.

For the binary dependent variable, a Fully Conditional Specification (FCS) logistic regression method is chosen for the imputer model considering the convenience of including dichotomous predictors. Baseline fibrosis stage (2 vs. 3), baseline T2DM (No/Yes), baseline BMI (as

Novartis
SAP

categorical predictor) and decrease of ALT at week 24 ( $\leq$  -17 U/L vs.  $\geq$ -17 U/L) will be included as predictors for the imputer's model.

The exclusion of treatment from the imputer model ensures a more conservative estimate of treatment effect in that it would bias only toward null (for superiority test) if a relationship between treatment and response does exist (Schafer 1997). The inclusion of decrease in ALT at week 24 (<= -17 U/L vs. >-17 U/L) into the imputer's model is based on findings by Loomba et. al. (2019) and considering the balance between general validity of analysis model and some loss in precision in case a trivial factor is additionally added in imputer's model (Rubin 1996).

If a reduced logistic regression model has to be adopted (Section 2.5.2), the reduced list of predictors in primary analysis model will also be used for the imputer model, except for the treatment which will still be excluded.

The imputer's model is first fitted using observations  $(n_0)$  with non-missing data

logit (p) = 
$$\beta^{T} \mathbf{X}$$

where

p is the true probability of response

**X** is the  $n_0$  by p matrix of covariates

 $\beta$  is the vector of coefficients to be estimated as the first step of MI.

Based on the estimated regression coefficients  $\hat{\beta}$  and associated covariance matrix, posterior predictive distribution for  $\beta$  is built and a new set of parameters  $\beta_{\#}$  is randomly sampled from it.

For *i*th patient with missing data, expected probability  $q_i = \Pr$  (response) is calculated as

$$q_i = \frac{\exp(\boldsymbol{\beta}_{\#}^{\mathsf{T}} \boldsymbol{X}_i)}{1 + \exp(\boldsymbol{\beta}_{\#}^{\mathsf{T}} \boldsymbol{X}_i)}$$

and this patient's response status will be imputed as Yes if  $q_i$  is larger than a random number sampled from uniform distribution between 0 and 1.

These imputation steps can be implemented using SAS MI procedure. A total of  $\geq$ =50 iterations of imputations will be executed to create 50 imputed complete data sets.

The logistic regression model for primary or key secondary analysis is then executed separately for these data sets with results (parameter estimates) stored in an output data set.

The SAS MIANALYZE procedure reads in the parameter estimates, standard errors or covariance matrix in the output data set generated by the logistic regression analyses, and produces estimates and 95% confidence limits to back calculate the odds ratios (95% CI). P-values will be presented if formal hypothesis test is to be performed according to hierarchical testing procedure outlined in Sections 2.5 and 2.6.

